#### 3.1.2. Part B

Part B will comprise a multiple-ascending dose, sequential-group design. Overall, it is planned for 24 subjects to be studied in 3 groups (Groups B1 to B3), with each group

consisting of 8 subjects. Part B may start following review of the safety and tolerability and PK data for Group A4, at a dose equal or less than given in Groups A1 to A4, provided the predicted exposure is not expected to exceed an exposure already shown to be safe and well tolerated. The dose level cannot be equal to a dose level from Part A if that dose met any of the dose escalation stopping rules.

Potential subjects will be screened to assess their eligibility to enter the study within 28 days prior to the first dose administration. Each subject will participate in 1 treatment period only and reside at the CRU from Day -1 until the morning of Day 12. All subjects will return for a Follow-up visit 7 to 10 days after their final dose.

[figure not shown]
Based on the ongoing review of available safety, tolerability, and PK data, up to 3 additional non-residential visits may be required. The number of additional visits per subject will not exceed 3 and will not extend beyond 28 days after each final dosing occasion.

In each of Groups B1 to B3, 6 subjects will receive AM1476 and 2 subjects will receive placebo. The dietary state for dosing in Part B will be subject to review of the PK data from the fed/fasted comparison in Part A. For all subjects, dosing is planned to be QD on Days 1 to 10, inclusive. However, the dietary state (including fasting requirement and meal compositions), dosing duration, and dosing frequency may be changed following review of safety, tolerability, and PK data from Part A or earlier groups in Part B (Section 3.4). The dose regimen will comprise no less than once every 2 days and will not exceed BID dosing. The predicted total daily exposure at the selected dose administered will not exceed an exposure shown to be safe and well-tolerated in Part A. The dosing duration will comprise no fewer than 7 consecutive days and will not exceed 28 consecutive days. There will be a minimum of 6 days between dose escalations for each group.

The total duration of study participation for each subject (from Screening through Follow-up visit) is anticipated to be approximately 7 weeks.

An overview of the study design is shown in Figure 4, and the planned dose levels in Figure 5. A Schedule of Assessments is presented in Appendix 7.

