3. STUDY ENDPOINTS

3.1. Primary Endpoints

The primary safety endpoints for this study are as follows:

- incidence and severity of adverse events (AEs)
- incidence of laboratory abnormalities, based on haematology, clinical chemistry, coagulation, and urinalysis test results
- vital signs measurements
- 12-lead electrocardiogram (ECG) parameters
- telemetry
- neurological examinations
- Columbia-Suicide Severity Rating Scale (C-SSRS)
- physical examinations.

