8.6. Safety and Tolerability Assessments

8.6.1. Adverse Events

All AEs will be coded using the Medical Dictionary for Regulatory Activities (MedDRA) Version 23.1 (or higher if a new version is issued during the study; see the DMP for more details).

A treatment-emergent adverse event (TEAE) will be defined as an AE that starts during or after the first dose, or starts prior to the first dose and increases in severity after the first dose.

A treatment-related TEAE will be defined as a TEAE with a relationship of possibly related or related to the study treatment, as determined by the investigator.

All AEs will be listed. In addition to the data recorded in the database, the listings will include derived onset time and duration. Onset time will be calculated from the time of the last associated dose for TEAEs only. Where the last associated dose is referring to the last dose received prior to the start of a TEAE.

The frequency of subjects with TEAEs and the number of TEAEs will be summarised for the following categories:

- TEAEs (overall, serious, leading to discontinuation, and leading to death) by treatment
- TEAEs by severity and treatment
- Treatment-related TEAEs (overall, serious, leading to discontinuation, and leading to death) by treatment
- Treatment-related TEAEs by severity and treatment

The frequency of subjects will be summarised separately for TEAEs and treatment-related TEAEs by the following:

- System organ class, preferred term, and treatment
- Preferred term and treatment

For the AE data the following rules will apply:

- For the derivation of relationship (applicable to AEs captured on the 'change in the severity' eCRF form only): The relationship to study treatment is not captured on the AE change in severity eCRF form because it is always assumed to be the same as the relationship captured on the first eCRF form completed for this AE (initial severity). Therefore, for these cases the missing relationship will be set to that captured on the first form completed for this AE.
- For the derivation of treatment-emergent status (applicable to all AEs): If the start date/time of an AE is incomplete or missing, an AE will be assumed to not be a TEAE, unless the incomplete start date/time or the end date/time indicates an AE started after the first dose.

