- For the derivation of treatment-related status (applicable to TEAEs only): If the study treatment relationship for a TEAE is missing, a TEAE will be assumed to not be a treatment-related TEAE.
- For the derivation of onset time (applicable to TEAEs only): If the start date/time of a TEAE is missing, onset time will not be calculated. If the start date/time of a TEAE is incomplete, where possible, the minimum possible onset time will be calculated and presented in '≥DD:HH:MM' format (eg, if the date/time of the last associated dose is 01MAY2019/08:00 and recorded start date/time of a TEAE is 03MAY2019, then the minimum possible onset time will be calculated by assuming a TEAE started at the first hour and minute of 03MAY2019 [03MAY2019/00:00], thus will be presented as onset time ≥01:16:00 in the listing). If the start date of a TEAE is the same as the date of the last associated dose but the start time of a TEAE is missing, an onset time will be presented as '≥00:00:01'. Any clock changes will be accounted for in the derivation.
- For the derivation of duration (applicable to all AEs): If the end date/time of an AE is missing, duration will not be calculated. If the start or end date/time of an AE is incomplete, where possible, the maximum possible duration will be calculated and presented in '≤DD:HH:MM' format (eg, if the start of an AE date/time is 01MAY2019/08:00 and its recorded end date/time is 03MAY2019, then the maximum possible duration will be calculated by assuming an AE ended at the last hour and minute of 03MAY2019 [03MAY2019/23:59], thus will be presented as duration ≤02:15:59 in the listing). Any clock changes will be accounted for in the derivation.
- For the calculation of TEAE summary statistics: If the severity of a TEAE is missing, that TEAE will be counted under the 'missing' category.

• For the calculation of TEAE summary statistics: If a subject experienced multiple TEAEs with the same preferred term for the same treatment, this will be counted as 1 TEAE for that treatment under the maximum severity recorded.

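### The SAP's number of TEAEs counts subject-by-term-by-treatment combinations, not events, so no summary table shows recurrence under repeated dosing

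*SAP*

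**What the plan says.** SAP Section 8.6.1 names two statistics: "The frequency of subjects with TEAEs and the number of TEAEs will be summarised for the following categories". The categories are TEAEs overall, serious, leading to discontinuation and leading to death; TEAEs by severity; and the same set again for treatment-related TEAEs, all by treatment.

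The tables by system organ class and preferred term are narrower and give subjects only: "The frequency of subjects will be summarised separately for TEAEs and treatment-related TEAEs by the following".

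The section ends with a counting rule. Its scope is set by its opening, "For the calculation of TEAE summary statistics: If a subject experienced multiple TEAEs", and no statistic is exempted. Its content is: "If a subject experienced multiple TEAEs with the same preferred term for the same treatment, this will be counted as 1 TEAE for that treatment", and the single count is placed "under the maximum severity recorded".

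For Part B, Protocol Section 3.1.2 says: "For all subjects, dosing is planned to be QD on Days 1 to 10, inclusive". SAP Table 3 gives each active Part B group one treatment label, so all dosing days in a group are the same treatment for this rule.

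Section 8.6.1 also says that every AE will be listed, with derived duration and, for TEAEs, onset time from the last associated dose.

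**The concern.** One count per subject and term at maximum severity is the usual rule for a subject-frequency column. Here the unit being counted is the TEAE, and the rule covers every TEAE summary. A column presented as the number of events would therefore hold something else.

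The primary objective includes the tolerability of multiple doses. A reaction that returns after each daily dose is a different tolerability finding from one transient episode. Subject counts ignore recurrence by design, and the preferred-term tables hold only subject counts. The event count is therefore the one planned AE summary that could reflect recurrence, and the rule removes it there. The severity split of the event count changes too, because all but the worst episode of a term drop out.

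**Working it through.** The plan gives no figure to reproduce, so the check applies the rule as written.

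**Inputs from the documents**
- n = 6 active subjects per Part B group (Protocol Section 3.1.2).
- D = 10 doses, once daily on Days 1 to 10 (same section).
- At most 1 TEAE per subject, preferred term and treatment, at maximum severity (SAP Section 8.6.1).

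**Assumptions, not in the documents**
- p is the chance of an episode of one preferred term after a dose. It is ranged from 0.05 to 1.0, equal for all subjects and independent between doses.
- Each recurrence is recorded as a separate AE.

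**Formulas**
- Expected episodes: E = n × D × p
- Expected count under the rule: C = n × [1 − (1 − p)^D]
- Undercount: E / C

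Example at p = 0.1: E = 6 × 10 × 0.1 = 6.0; C = 6 × (1 − 0.9^10) = 3.91; E / C = 1.54.

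| p | Episodes E | Counted C | E / C |
|---|---|---|---|
| 0.05 | 3.0 | 2.41 | 1.25 |
| 0.1 | 6.0 | 3.91 | 1.54 |
| 0.3 | 18.0 | 5.83 | 3.09 |
| 0.5 | 30.0 | 5.99 | 5.0 |
| 1.0 | 60.0 | 6.0 | 10.0 |

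C cannot exceed 6 per term and is close to 6 from p = 0.3 upwards. The count therefore separates one-off from recurrent reactions least well when recurrence is heaviest. If all 6 subjects have one episode each, the table shows 6 subjects and 6 TEAEs. If all 6 have ten episodes each, it shows the same.

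**Severity split.** A subject with nine mild episodes and one moderate episode of a term contributes 0 mild and 1 moderate TEAE.

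**A smaller effect in Part A.** SAP Table 1 pools placebo over fasting conditions but gives Group A3 active separate fasted and fed labels. The same term in both periods counts once for a placebo subject but once under each label for an active subject. The two event counts are then not on the same footing.

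**The case against.** The strongest reply is that little is lost. All AEs are listed with duration, and TEAEs with their timing from the last dose. With 6 active subjects in a group, a reaction recurring after each dose can be read from the listing. The primary AE endpoint is incidence and severity. The number of subjects affected and the worst severity per subject and term are unchanged, so the worst event is never understated. SAP Section 8.6.6 plans no inferential safety analysis. Under Protocol Section 3.6, escalation rests on ongoing review of available data and interim safety reports, not on these final tables. All of this stands. A reader might infer that the plan hides recurrent reactions or undermines the primary endpoint; the documents do not support either reading. The gap is confined to the summary tables.

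The large multiples are also ceilings. Ten-fold needs every subject to react after every dose. A reader might go further: dosing may be twice daily and "will not exceed 28 consecutive days", which allows 2 × 28 = 56 doses and a 56-fold undercount. That is the outer limit of what is permitted. The alternatives that Protocol Section 3.4 describes are twice daily over 7 days (14 doses) and once daily over 28 days (28 doses). No event rate is given, so no multiple is a forecast.

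The rule may be meant to stop severity-change forms of one AE being counted twice, or to apply only to subject counts. The table shells, which were not available for this review, may label the column differently. The SAP text makes neither limitation, and it is the text that defines the statistic.

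Finally, counting episodes in the overall rows alone would not show which term recurred, because the preferred-term tables carry no event numbers. That is correct, and the fix takes it into account.

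**Conclusion.** The point holds for the event counts. As written, the number of TEAEs is the number of distinct subject, preferred term and treatment combinations, and its severity split follows the worst episode only. No other passage in the SAP or protocol defines the event count differently, and no summary table would show recurrence in Part B.

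For one term in one active group on the planned regimen, the expected undercount is about 1.25-fold at p = 0.05, 1.5-fold at 0.1 and 3.1-fold at 0.3, with a ceiling of 10-fold. If nothing recurs there is no undercount. These figures rest on an assumed p that is equal across subjects and independent across doses, and on each recurrence being recorded as its own AE; the documents do not settle how an intermittent reaction is recorded. The correction is worth making because the plan undertakes to report this number, but it does not call the primary safety conclusions into question.

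**What to change.** In SAP Section 8.6.1:
- Limit the one-per-term, maximum-severity rule to the subject-frequency counts.
- For the number of TEAEs, count each distinct AE episode. Merge the initial record and any severity-change records of one AE into a single episode at its maximum severity.
- Add the number of events to the preferred-term tables, for TEAEs and treatment-related TEAEs, so that recurrence of a given reaction can be seen.

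Relabelling or footnoting the column would remove the misnomer but would still leave recurrence out of every summary table.

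The cost is a short wording change, matching table shells and minor programming. No new data are needed. Event counts will be higher and look less favourable wherever a reaction recurs.

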8.6.2. Clinical Laboratory Parameters

All clinical laboratory parameters will be listed; any value outside the clinical reference range will be flagged. Separate listings will be provided for any parameter for which there is any individual subject value outside the respective clinical reference range.

Summary tables and boxplots by treatment and timepoint will be provided for clinical chemistry, haematology, and coagulation parameters.

Values recorded as $\langle x, \leq x, \rangle x$, or $\geq x$ will be displayed in the listings as recorded. For the derivation of listing flags, all calculations, and presentation in the figures, $\langle x$ and $\leq x$ values will be set to half of x, whereas $\rangle x$ and $\geq x$ values will be set to x.

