## 7.2.2. Clinical Laboratory Evaluations

Blood and urine samples will be collected for clinical laboratory evaluations at the times indicated in the Schedule of Assessments in Appendix 6 for Part A and Appendix 7 for Part B. Clinical laboratory evaluations are listed in Appendix 2. The maximum volume of blood withdrawn per subject will not exceed the limit detailed in Appendix 3. Additional clinical laboratory evaluations will be performed at other times if judged to be clinically appropriate or if the ongoing review of the data suggests a more detailed assessment of clinical laboratory safety evaluations is required.

Subjects will be asked to provide urine samples for drugs of abuse screen and cotinine test, and will undergo an alcohol breath test at the times indicated in the Schedule of Assessments in Appendix 6 for Part A and Appendix 7 for Part B. For all female subjects, a pregnancy test

will be performed at the times indicated in the Schedule of Assessments in Appendix 6 for Part A and Appendix 7 for Part B.

An Investigator (or designee) will perform a clinical assessment of all clinical laboratory data.

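### SAP 8.6.2 sets out-of-range laboratory flags from substituted values, so a result reported with an inequality can be flagged low without proof or left unflagged when certainly high

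*SAP*

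**What the plan says.** SAP 8.6.2 requires that "any value outside the clinical reference range will be flagged". It adds: "Separate listings will be provided for any parameter for which there is any individual subject value outside the respective clinical reference range". A result reported with an inequality sign "will be displayed in the listings as recorded".

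Behind the display, the result is replaced by a number. The replacement is used "For the derivation of listing flags, all calculations, and presentation in the figures". There is one rule for each side: for `<x` and `≤x`, "values will be set to half of x, whereas" for `>x` and `≥x` "values will be set to x".

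SAP 3.1 names among the primary endpoints "incidence of laboratory abnormalities, based on haematology, clinical chemistry, coagulation, and urinalysis test results". SAP 8.6.2 plans summary tables and boxplots for chemistry, haematology and coagulation, but not for urinalysis. It specifies no table counting laboratory abnormalities. SAP 8.6.6 rules out inferential analysis of safety data.

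**The concern.** Substituting a number for a censored result is an ordinary device for computing a mean or drawing a boxplot. A flag asks a different question: does the result lie outside the reference range? The recorded inequality often answers that exactly, and the substituted number can answer it wrongly.

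Two distinct errors are possible. The halving rule can mark a result low when it may be in range. The rule that sets `>x` to x can leave unmarked a result that is known to be high.

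Flags, and the separate listings that they trigger, are the only output in SAP 8.6.2 that shows out-of-range status. For urinalysis, listings are the only planned output of any kind. A wrong flag could therefore produce an out-of-range listing for a parameter with no demonstrated abnormality. A missed flag could leave a parameter without its listing, if that result were the parameter's only abnormal value.

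**Working it through.** **Inputs.** The substitution and flagging rules come from SAP 8.6.2. The documents give no reference ranges or reporting limits and do not say whether a limit counts as in range. All values of LLN, ULN and x below are therefore assumptions. A value equal to a limit is treated as in range: flag low if value < LLN, flag high if value > ULN. The plan states no figure to reproduce.

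**Low side, `<x` set to x/2.** The low flag is raised when x/2 < LLN, that is, when x < 2 × LLN. The flag is certain to be right only if every value below x is below LLN, that is, when x ≤ LLN. The flag may therefore be false when

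LLN < x < 2 × LLN.

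For `≤x` the band also includes x = LLN, where the flag is false only if the true value is exactly LLN.

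**High side, `>x` set to x.** The high flag is raised when x > ULN. Every possible true value is above ULN when x ≥ ULN. The two conditions differ only at

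x = ULN,

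where the result is certainly high and is not flagged.

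**Cases with assumed limits**

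| Recorded | LLN, ULN | Substituted | SAP flag | Possible true status |
|---|---|---|---|---|
| `<2` | 1, 10 | 1.0 | none | low or in range |
| `<2` | 1.5, 10 | 1.0 | low | low or in range |
| `<2` | 2, 10 | 1.0 | low | low only |
| `≤2` | 2, 10 | 1.0 | low | low, or in range if exactly 2 |
| `>10` | 2, 10 | 10 | none | high only |
| `≥10` | 2, 10 | 10 | none | in range if exactly 10, or high |
| `>10.5` | 2, 10 | 10.5 | high | high only |
| `>9` | 2, 10 | 9 | none | in range or high |

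The second and fourth rows show a low flag that may be false. The fifth shows the certain miss. The others are flagged correctly, or are unflagged with undetermined status.

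**Check across the range.** Stepping LLN/x from 0 to 2 by 0.01, a possibly false low flag for `<x` appears only from 0.51 to 0.99. Stepping x/ULN from 0.5 to 1.5 by 0.01, the certain missed high appears only at 1.00. Both agree with the algebra.

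**Conditional illustration in urinalysis.** Protocol Appendix 2 includes urine pH and specific gravity. Suppose the laboratory reports the floor of each scale with an inequality sign, which the documents do not say.

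- pH `≤5.0` becomes 5.0/2 = 2.5. With an assumed LLN of 5.0 it is flagged low, and the flag is wrong if the true pH is exactly 5.0.
- Specific gravity `≤1.005` becomes 1.005/2 = 0.5025. With an assumed LLN of 1.005 the flag is wrong only if the true value is exactly 1.005. With a lower assumed LLN that is still above 0.5025, it is wrong for any true value from that LLN to 1.005.
- If LLN lies above 5.0 or above 1.005 respectively, the low flag is correct.

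**The case against.** The strongest reply is that nothing in the documents shows either case arising. A possibly false low flag needs a reporting limit above LLN but below twice LLN. The certain miss needs a reporting limit exactly equal to ULN, with ULN counted as in range. No parameter in Protocol Appendix 2 is shown to meet either condition. This stands, and it keeps the point conditional.

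The consequences are also contained. The inequality stays visible in the full listing whether or not it is flagged. Protocol 7.2.2 provides that "An Investigator (or designee) will perform a clinical assessment of all clinical laboratory data", and that review is not stated to depend on the SAP's flags. Protocol Appendix 1 treats clinically significant abnormal laboratory findings as adverse events, which are summarised separately. This too stands, although none of it corrects a programmed flag.

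A reader might infer three stronger things that the documents do not support.

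- **That drug–placebo differences would be diluted.** No comparison or count of flags by treatment is planned, so there is nothing to dilute.
- **That half-x urine pH or specific gravity proves a wrong flag.** An impossible substituted value does not make the flag wrong; that depends on where LLN lies. Nor would the halved value reach a planned table or figure, since urinalysis is listed only, with the result as recorded.
- **That a true high result would be hidden.** At most the result loses its mark and, if it were the parameter's only out-of-range value, the extra listing is not produced. The result itself remains in the main listing.

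**Conclusion.** The rule is wrong as written, and minor. This is not a missing detail: SAP 8.6.2 explicitly bases flags on the substituted value, and for `>x` at an in-range ULN that contradicts its own instruction to flag whatever is out of range.

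The two errors have separate causes. Halving accounts only for the low side; the missed high comes from setting `>x` to x. Neither is general. The low flag is right for `<x` whenever x ≤ LLN, and the certain miss exists only at x = ULN.

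How many results would be affected cannot be estimated without the laboratory's reference and reporting limits. What is at stake is the accuracy of flags and supplementary listings for a descriptively reported primary endpoint. The documents do not support reading this as a subject-safety failure or as a bias in a treatment comparison.

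**What to change.** In SAP 8.6.2, derive listing flags from the recorded inequality, or use the laboratory's own flag:

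- low for `<x` only if x ≤ LLN, and for `≤x` only if x < LLN;
- high for `>x` if x ≥ ULN, and for `≥x` if x > ULN;
- otherwise no flag, with the result still shown as reported.

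State that a value equal to a reference limit counts as in range, which these rules assume. Keep the x/2 and x substitutions for numeric summaries and figures only. Under the change, `<2` with LLN 1.5 loses its unproven low flag and `>10` with ULN 10 gains a high flag. Cases already flagged correctly, such as `<2` with LLN 2 and `>10.5` with ULN 10, do not change.

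The cost is about two sentences in the SAP and a small programming change, with no effect on data collection. It is cheapest before programming starts, the point by which SAP Section 1 wants the plan and the output shells to be final.
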